6. TREATMENTS

The following is a list of the study treatment abbreviations that will be used in the TFLs.

Part A (Trained Users who have an accompanying person with T1DM or T2DM)

Study Treatment Name	Abbreviation	Treatment order in TFL
Nasal glucagon	NG	1
Glucagon emergency kit	GEK	2

Part B (Untrained Users)

Study Treatment Name	Abbreviation	Treatment order in TFL
Nasal glucagon	NG	3
Glucagon emergency kit	GEK	4

7. SAMPLE SIZE JUSTIFICATION

The sample size is 26 in each of the 2 cohorts (Trained Users and Untrained Users). It is assumed that the percentages of successful dosing of NG and GEK will be 90% and 50%, respectively.

Additionally, a proportion of discordant pairs of 45% is assumed, which reflects a moderate within-subject correlation between the 2 treatments.

These numbers are based on the Yale 2017 study³, where 15 out of 16 (93.8%) NG simulations were completely successful and 8/16 (50%) GEK administrations were partially or completely successful in the “caregivers” group (the equivalent of the Trained Users group in this study). Note that for GEK, the “partial or complete success” rate is used. In Yale 2017, only 2 out of 16 (12.5%) simulations were completely successful for the GEK treatment. Hence, we are using a best-case scenario approach for the successful administration rates of GEK in the current study. In conclusion, the 90% success rate for NG is based on the Yale 2017 NG success rate (15/16, 93.8%, rounded down) and the 50% success rate for GEK is based on the best-case scenario from the Yale 2017 study, i.e. partial administration of GEK in 8/16 (50%) simulations.

Based on these numbers, the sample size will provide 90% statistical power to detect a statistically significant difference between success rates of NG and GEK, using the test with a 2-sided alpha level of 0.05.

Enrollment will be continued per group until 26 Trained Users have been recruited (stratified into 13 who have an accompanying PWD with T1DM, and 13 who have a PWD with T2DM) and 26 Untrained Users have been recruited.

Participants who are randomized but do not participate in the study simulations may be replaced to ensure that enough participants may complete the study.

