To assess the number of simulations that result in successful administration of NG.	The percentage of all simulations that result in a successful administration of NG, for all users combined.

Objectives	Endpoints
To assess whether, overall, one device (NG or GEK) is preferred over the other.	The percentage of participants (Trained Users, PWDs and Untrained Users) that prefer one device over the other, as recorded in a questionnaire.
To assess overall ease of use of both devices (NG and GEK).	The 'ease of use' questionnaire ratings given to NG and to GEK by Trained Users, PWDs and Untrained Users.

Summary of Study Design:

Study I8R-MC-IGBM is a single-center, crossover study assessing the use of NG and GEK during a simulation of a severe hypoglycemia episode, with 2 cohorts of participants: Trained Users (Part A) and Untrained Users (Part B).

Each participant will take part in 2 simulations, 1 with NG and 1 with GEK. Quantitative results (whether or not a dose is administered successfully, and how long it takes) will be recorded by site staff during each simulation.

Qualitative results (the opinions of Trained Users, Untrained Users and PWDs) will be captured via questionnaires, both during and at the end of the study.

Study Arms and Planned Duration for an Individual Participant:

In **Part A**, each Trained User and the accompanying PWD will attend 3 one-day study visits, over the course of approximately 2 weeks:

- An initial training visit
- Two study visits, each involving a simulation of a severe hypoglycemia emergency, which the Trained User will attempt to treat with NG and GEK in turn (in randomized order).

In **Part B**, each Untrained User will attend 2 study visits over the course of approximately 1 week. Each visit will include 1 simulated severe hypoglycemia emergency, which the participant will attempt to treat with NG and GEK in turn (in randomized order).

Number of Participants:

Approximately 72 participants (39 Trained Users and 33 Untrained Users) will be recruited to ensure that 52 participants (26 Trained Users and 26 Untrained Users) complete the study.

Trained Users will be recruited such that, of the completers, half (i.e. at least 13) of the accompanying PWDs have type 1 diabetes mellitus (T1DM), and half (at least 13) have type 2 diabetes mellitus (T2DM).

Each Trained User will be accompanied at each visit by the PWD with whom they are recruited to the study.

Statistical Analysis:

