5.1.3.2. Part B (Untrained Users)

Untrained Users will attend the site for 2 visits ([Figure IGBM.2](#)).

At **Visit 1**, after being evaluated for eligibility and giving informed consent, each Untrained User will be randomized to 1 of 2 schedules ([Table IGBM.2](#)), which will determine the device used at each simulation. Male manikins will be used in each case.

Each Untrained User will be given a brief explanation of diabetes and severe hypoglycemia, and briefly shown an example of Device 1 (NG or GEK depending on randomization). No instruction will be given on how to use the device; nor will the Untrained User be allowed time to read any instructions for using the device.

Each Untrained User will then take part in a simulation (see Section [5.1.3.3](#)) using Device 1. Staff will assess successful or unsuccessful treatment (Section [5.1.3.4](#)), and time to successful administration (if this occurred within the allotted time). After a short rest period, the Untrained User will complete the NASA TLX questionnaire about their experience.

At **Visit 2**, approximately 7 days after Visit 1, each Untrained User will be shown an example of Device 2. As at Visit 1, no instruction will be given on how to use the device. The Untrained User will take part in a simulation using Device 2, and then complete the NASA TLX. Site staff will assemble a video of both simulations, and the Untrained User will watch it. After a delay of 55 to 60 minutes, the Untrained User will fill in a questionnaire comparing both devices, and then individual-device questionnaires in randomized order ([Table IGBM.2](#)). Details of the questionnaires are in Section [9.10](#). The Untrained User will be given a device-specific questionnaire only if they attempted to administer that device. For example, there will be no questionnaire for a simulation if insulin was wrongly administered instead of the glucagon device, or if no attempt was made to administer a device. Similarly, Untrained Users will be given the comparative questionnaire only if they attempted to administer both NG and GEK devices during the respective simulations.

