5.2. Number of Participants

Approximately 72 participants (39 Trained Users and 33 Untrained Users) may be enrolled so that approximately 52 participants (26 Trained Users and 26 Untrained Users) complete the study.

Each Trained User must be accompanied during each visit by the PWD with whom they are associated (see Section 6.1). Trained Users will be recruited such that, of completers, half (i.e. at least 13) of the accompanying PWDs have T1DM, and half (at least 13) have T2DM.

For purposes of this study, a participant completes the study when all scheduled procedures shown in the Schedule of Activities (Section 2) have been completed.

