Appendix 1. Abbreviations and Definitions

Term	Definition
ADA	American Diabetes Association
AE	adverse event: Any untoward medical occurrence in a patient or clinical investigation subject administered a pharmaceutical product that does not necessarily have a causal relationship with this treatment. An AE can therefore be any unfavorable and unintended sign (including an abnormal laboratory finding), symptom or disease temporally associated with the use of a medicinal (investigational) product, whether or not related to the medicinal (investigational) product.
Complaint	A complaint is any written, electronic or oral communication that alleges deficiencies related to the identity, quality, purity, durability, reliability, safety or effectiveness, or performance of a drug or drug delivery system.
Compliance	Adherence to all the study-related requirements, good clinical practice (GCP) requirements, and the applicable regulatory requirements.
CRF	case report form
CRP	clinical research physician: Individual responsible for the medical conduct of the study. Responsibilities of the CRP may be performed by a physician, clinical research scientist, global safety physician or other medical officer.
Enroll	The act of assigning a participant to a randomization schedule.
Enter	Subjects entered into a study are those who sign the informed consent form.
ERB	ethical review board
GCP	good clinical practice
GEE	generalized estimating equation
GEK	glucagon emergency kit
ICF	informed consent form
ICH	International Council for Harmonisation
IFU	Instructions for Use
informed consent	A process by which a subject voluntarily confirms his or her willingness to participate in a particular study, after having been informed of all aspects of the study that are relevant to the subject's decision to participate. Informed consent is documented by means of a written, signed and dated informed consent form.
investigational product	A pharmaceutical form of an active ingredient or placebo being tested or used as a reference in a clinical study, including products already on the market when used or assembled (formulated or packaged) in a way different from the authorized form, or marketed products used for an unauthorized indication, or marketed products used to gain further information about the authorized form.

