3. INTRODUCTION

This SAP has been developed after review of the Clinical Study Protocol (final version dated 21 September 2018).

This SAP describes the planned analysis of the efficacy and safety data from this study. A detailed description of the planned TFLs to be presented in the clinical study report (CSR) is provided in the accompanying TFL shell document.

The intent of this document is to provide guidance for the statistical analysis of data. In general, the analyses are based on information from the protocol, unless they have been modified by agreement between Eli Lilly and Company and Covance Early Clinical (EC) Biometrics. A limited amount of information concerning this study (e.g., objectives, study design) is given to help the reader's interpretation. This SAP must be signed off prior to first subject simulation for this study. When the SAP and TFL shells are agreed upon and finalized, they will serve as the template for this study's CSR.

This SAP supersedes the statistical considerations identified in the protocol; where considerations are substantially different, they will be so identified. If additional analyses are required to supplement the planned analyses described in this SAP, they may be performed and will be identified in the CSR. Any substantial deviations from this SAP will be agreed upon between Eli Lilly and Company and Covance EC Biometrics and identified in the CSR. Any minor deviations from the TFLs may not be documented in the CSR.

This SAP is written with consideration of the recommendations outlined in the International Conference on Harmonisation (ICH) E9 Guideline entitled Guidance for Industry: Statistical Principles for Clinical Trials¹ and the ICH E3 Guideline entitled Guidance for Industry: Structure and Content of Clinical Study Reports².

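### Does closing enrolment at 26 recruits per cohort undercut a power statement that needs 26 completers?

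*SAP*

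**What the plan says.** SAP Section 7 and Protocol Section 10.1 share the same sentence: "Enrollment will be continued per group until 26 Trained Users have been recruited", split into 13 whose person with diabetes has type 1 and 13 whose person has type 2. The same count of 26 applies to Untrained Users. The next sentence in both places reads "Participants who are randomized but do not participate in the study simulations may be replaced", and gives the purpose as having enough people finish the study.

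The protocol synopsis says "Approximately 72 participants (39 Trained Users and 33 Untrained Users) will be recruited to ensure that 52 participants" (26 in each cohort) complete. Section 5.2 is more permissive: "Approximately 72 participants (39 Trained Users and 33 Untrained Users) may be enrolled so that approximately 52 participants" complete. Both add that at least 13 completers in Part A should be paired with a person with type 1 diabetes and at least 13 with a person with type 2. Section 5.2 also says that "a participant completes the study when all scheduled procedures shown in the Schedule of Activities (Section 2) have been completed".

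Three other statements bear on the point:

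- Protocol Appendix 1 defines enrolling as "The act of assigning a participant to a randomization schedule".
- SAP Section 3 says "This SAP supersedes the statistical considerations identified in the protocol".
- SAP Section 9.5 makes McNemar's test the primary analysis, with an exact sign test as sensitivity analysis.

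**The concern.** The same verb, recruited, is attached to 39 Trained Users in the synopsis and to 26 in the sample-size sections. The counts differ by 39 − 26 = 13 Trained Users and 33 − 26 = 7 Untrained Users, or 72 − 52 = 20 in all.

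McNemar's test uses only participants with a result on both devices. Randomization happens at Visit 1. The two simulations fall at Visits 2 and 3 in Part A and at Visits 1 and 2 in Part B. If enrolment closed at 26 randomized, anyone lost before the second simulation would leave fewer than 26 pairs, and the stated 90% power would no longer be assured.

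Replacement is worded as optional. It does not plainly cover a participant who does the first simulation and misses the second. The SAP also claims precedence over the protocol's statistical text but does not repeat the 39 and 33.

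**Working it through.** **Inputs** (SAP Section 7, repeated in Protocol Section 10.1): success 90% with NG and 50% with GEK, 45% discordant pairs, two-sided alpha 0.05, n = 26 pairs, stated power 90%.

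Let a be the probability that only NG succeeds and b the probability that only GEK succeeds. Then a + b = 0.45 and a − b = 0.40, so a = 0.425 and b = 0.025.

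**Reproducing the plan's figure.** The normal formula for McNemar's test is

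power = Φ[(0.40·√n − 1.96·√0.45) / √(0.45 − 0.40²)].

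At n = 26: (2.040 − 1.315) / 0.5385 = 1.346, so power is 91.1%.

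Solved for 90% power: n = [(1.96·√0.45 + 1.2816·√0.29) / 0.40]² = 25.1, which rounds up to 26.

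Full enumeration over the number of discordant pairs (binomial with probability 0.45) and their split (probability 0.425/0.45 in favour of NG) gives 90.8% for the exact test and 94.8% for the uncorrected asymptotic test. The stated 90% is therefore correct, and it is a statement about 26 complete pairs.

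**If losses were never replaced:**

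| Complete pairs | Exact | Formula | Asymptotic |
|---|---|---|---|
| 26 | 90.8% | 91.1% | 94.8% |
| 25 | 89.3% | 89.8% | 93.9% |
| 24 | 87.5% | 88.4% | 92.9% |
| 23 | 85.5% | 86.9% | 91.8% |
| 22 | 83.2% | 85.1% | 90.4% |
| 21 | 80.5% | 83.2% | 89.0% |
| 20 | 77.4% | 81.1% | 87.3% |

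Exact and asymptotic results are both shown because SAP Section 9.5 names McNemar's test while its example code also requests the exact version. A participant who misses a simulation is assumed to contribute no pair.

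**Which rule do the documents set?**

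- Target: 26 completers per cohort (synopsis and Section 5.2).
- Allowance: about 39 and 33. No dropout rate is stated. The figures leave room for losses of 1 − 26/39 = 33.3% and 1 − 26/33 = 21.2%.
- Mechanism: replacement so that enough participants finish (Section 10.1 and SAP Section 7).
- Split: the 13/13 attached to the 26 in SAP Section 7 is the split that Section 5.2 requires among completers. If 26 were a cap on randomization, a single Part A loss would break that requirement and the figure of 39 would have no purpose.

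Only one reading gives every sentence a function: 26 is the number to be delivered, and 39 and 33 are the room for delivering it.

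**The case for a change.** The strongest case is that no single sentence states the combined rule, and that a site reading SAP Section 7 alone could stop too soon. At the loss rates implied by 39 and 33, with nothing replaced, Part A would keep about 26 × 26/39 ≈ 17 pairs. Power would then be 65.1% exact, 73.3% by the formula and 81.1% asymptotic. Part B would keep 20 or 21 pairs, with exact power of 77.4% to 80.5%. By the exact test and the formula, 26 is the smallest n that reaches 90%, so there is no slack on those two methods.

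The arithmetic stands, but the scenario undermines itself. It takes its loss rate from the planned 39 and 33 and then assumes that those participants are never enrolled.

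The supporting arguments are weaker:

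- **Precedence of the SAP.** It covers statistical considerations, and Protocol Section 10.1 carries the same two sentences as SAP Section 7, so nothing is overridden. The enrolment allowance sits in the synopsis and Section 5.2, and SAP Section 3 says that it repeats only limited design information.
- **The glossary.** It defines enrolling but not recruiting, so reading 26 recruited as 26 randomized is an inference.
- **A participant lost after one simulation.** This person is not a completer under Section 5.2, so the allowance for reaching 26 completers already covers the loss. The replacement sentence does not mention the case, but does not exclude it.
- **Failed simulations.** Section 5.1.3.2 says "there will be no questionnaire for a simulation if insulin was wrongly administered instead of the glucagon device", and Section 5.1.3.1 agrees. One might fear that such a participant counts as a non-completer and is replaced, which would make replacement depend on the outcome. But replacement is limited to people who took no part in the simulations, and this person did take part. The missing questionnaire is one that the protocol itself withholds.

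What remains is that the word recruited is loose in two sections.

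**Conclusion.** This is a clerical slip that the rest of the plan resolves. The target of 26 completers, the 39/33 allowance, the 13/13 split among completers and the replacement provision all point the same way. A sponsor working from the whole plan reaches 26 pairs per cohort, where power is 90.8% (exact), 91.1% (formula) or 94.8% (asymptotic) against the stated 90%.

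Even a small lapse would cost little. One unreplaced loss leaves exact and formula power less than one point under 90%, and asymptotic power stays at or above 90% down to 22 pairs. The 50% GEK rate is also described in the plan as a best case, against 12.5% complete success in the cited study, so the planning difference is cautious; I put no figure on that.

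The conclusion rests on the plan's 90%, 50% and 45% assumptions and on losses being replaced for the purpose the plan gives. Making replacement mandatory would be a new design choice, not a correction. No number, analysis or interpretation would change, so no amendment is warranted.

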8. DEFINITION OF ANALYSIS POPULATIONS

The “Full Analysis Set” will consist of all subjects who participate in at least one training of a study device.

The “Per Protocol Population” will consist of all subjects who complete the study without major protocol deviations.

All protocol deviations that occur during the study will be considered for their severity/impact and will be taken into consideration when subjects are assigned to analysis populations.

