4.2 Secondary Objectives

- To test the hypothesis that more Untrained Users can successfully administer NG than GEK when treating a simulated episode of severe hypoglycemia.
- To compare the average time to successfully administer NG, compared with GEK, for trained and untrained users.
- To compare percentages of users who complete critical administration steps for both NG and GEK, for trained and untrained users.
- To assess the number of simulations that result in successful administration of NG.
- To assess whether, overall and for trained users, persons with diabetes (PWDs) and untrained users, one device (NG or GEK) is preferred over the other.
- To assess overall, and for trained users, PWDs and untrained users, ease of use of both devices (NG and GEK).

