5.1 Types of Participants

Participants are defined as follows:

- **Trained User:** A participant who, during the study, will be given a level of training intended to mimic that of a real-life caregiver, relative, or close friend of a PWD.
 - “Trained User” participants must be either related to, or a close friend of, a PWD, and therefore already familiar with diabetes and the risk of severe hypoglycemia. Each Trained User must be recruited alongside the PWD with whom they are familiar, as a “dyad” (a pair of people who have a pre-existing relationship).
 - The Trained User will receive instruction on the use of each device, from the PWD, before taking part in the simulation using that device.
 - Trained Users must not have actually administered injectable glucagon (or another rescue medication) in the past. However, they may own a glucagon rescue kit, and may have been instructed in its use, as long as such instruction occurred at least 2 years before screening.
- **PWD:** The PWD who is the close friend or relative of the Trained User.
 - During the study, the PWD will be trained by site staff on the use of each device, and at least 7 days before each simulation, will relay these instructions to the Trained User.
 - The PWD previously may have been instructed in the use of a glucagon rescue kit, as long as such instruction occurred at least 2 years before screening.
- **Untrained User:** A participant who will not be given training during the study on either device, and who has limited knowledge of severe hypoglycemia and how to treat it.
 - These participants are intended to approximate a real-life colleague or acquaintance of a PWD: someone who is aware of the PWD’s condition and is willing to intervene in an episode of severe hypoglycemia, but has not received instructions. Untrained Users in this study may or may not know a PWD in real life. In any case, they must not have caregiving responsibilities toward a PWD.
 - Untrained Users will participate in the study alone (not as part of a dyad).
 - Prior to the simulations in this study, Untrained Users will be given basic information about severe hypoglycemia and briefly shown an example of each rescue device.

[Figure 1](#) (Part A) and [Figure 2](#) (Part B) illustrate the study design.

[figure not shown]
[figure not shown]

Figure 1 - Illustration of study design for Part A.

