9. STATISTICAL METHODOLOGY

9.1 General

Data listings will be provided for all data that is databased. Summary statistics and statistical analysis will only be presented for data where detailed in this SAP. For continuous data, summary statistics will include the arithmetic mean, arithmetic standard deviation, median, min, max, P25, P75 and N will also be presented. For categorical data, frequency count and percentages will be presented. Data listings will be provided for all subjects up to the point of withdrawal, with any subjects excluded from the relevant population highlighted. Summary statistics and statistical analyses will generally only be performed for subjects included in the relevant analysis population. For the calculation of summary statistics and statistical analysis, unrounded data will be used.

Data analysis will be performed using SAS® Version 9.4 or greater.

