- 2 minutes-2 minutes 15 seconds
- 2 minute 15 seconds-2 minutes 30 seconds
- 2minutes 30 seconds-2 minutes 45 seconds
- 2 minutes 45 seconds-3 minutes
- 3-4 minutes
- 4-5 minutes
- 5-10 minutes
- >10 minutes

A graphical presentation of the successful administration times will be provided using a Kaplan-Meier plot.

To simultaneously model the training effect (Trained Users versus Untrained Users) and the treatment effect (NG versus GEK), a generalized estimating equations (GEEs) model will be performed, with treatment, training and the treatment-by-training interaction effect as independent variables, and the participant as participant identifier. As each Trained User and Untrained User will perform both the NG and the GEK administration, the data are paired for the device type but not paired for the level of training. Using a GEE model will enable estimation of both effects simultaneously, and also estimation of the interaction effect, which will test whether the difference between devices varies between Trained Users and Untrained Users. Furthermore, the randomization order (NG-GEK versus GEK-NG) can be tested within this model. Given the low sample size of this study and multitude of variables that can be entered, this GEE modelling will be exploratory in nature.

Primarily, a GEE model using the binary distribution (success versus no success) and the identity link will be produced: this will produce estimated rate differences with 95% confidence intervals. In case this model fails to converge, log or logit links can be attempted, to estimate relative risks or odds ratios, respectively.

Example SAS code:

```
proc genmod data=xx descending;
class subjid arm trt ftrt ;
model success = arm|trt ftrt / link=identity dist=bin;
repeated subject=subjid;
lsmeans arm*trt / ilink diff;
lsmeans arm / ilink diff;
lsmeans trt / ilink diff;
lsmeans ftrt / ilink diff;
run;
```

where arm = trained or untrained, trt = NG or IM and ftrt = first treatment received

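### The Full Analysis Set requires device training, so as written it contains none of the Untrained Users whom the SAP plans to analyse

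*SAP*

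**What the plan says.** SAP Section 8 defines two sets. The FAS "will consist of all subjects who participate in at least one training of a study device". The Per Protocol Population is made up of those who finish the study without major deviations. One FAS rule covers both cohorts.

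SAP Section 5.1 defines an Untrained User as "A participant who will not be given training during the study on either device". Protocol Section 5.1.3.2 is just as firm about Part B: "No instruction will be given on how to use the device; nor will the Untrained User be allowed time to read any instructions". The Part B schedule in Protocol Section 2 has no training row; the Part A schedule does.

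The SAP nevertheless plans to analyse Part B. Its first secondary objective is "To test the hypothesis that more Untrained Users can successfully administer NG than GEK when treating a simulated episode of severe hypoglycemia". Section 9.5 lists the matching comparison and a GEE model intended to give "estimation of the interaction effect, which will test whether the difference between devices varies between Trained Users and Untrained Users".

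The only link between analyses and sets is in SAP Section 9.1: "Summary statistics and statistical analyses will generally only be performed for subjects included in the relevant analysis population". No section says which set is the relevant one. Protocol Section 10.2 covers disposition and participant characteristics but defines no analysis sets.

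**The concern.** Entry to the FAS depends on an event that Part B is designed to withhold, so the definition fits Part A only. Anyone who applies the FAS as written to Part B gets an empty set for a pre-stated secondary hypothesis and for every contrast between trained and untrained people.

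The rule is also too wide at the other end. It admits Trained Users who are trained at Visit 1 and never reach a simulation, a case the SAP foresees: "Participants who are randomized but do not participate in the study simulations may be replaced". Read literally, it could also admit the accompanying persons with diabetes (PWDs), because "the PWD will be trained by site staff on the use of each device", although they never perform a simulation. Neither group has a success outcome, so the denominator for the success percentages is unclear.

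What is at stake is pre-specification. The study is open-label. If the definition stays as it is, the set for Part B has to be settled by someone's judgement, possibly after outcomes are known.

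**Working it through.** **1. The plan's own power figure.** Inputs from SAP Section 7: success 90% (NG) and 50% (GEK), discordant pairs 45%, n = 26 per cohort, two-sided alpha 0.05. Let p10 be the probability that only NG succeeds and p01 the probability that only GEK succeeds.

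- p10 + p01 = 0.45 and p10 − p01 = 0.90 − 0.50 = 0.40, so p10 = 0.425 and p01 = 0.025.
- Power of the exact McNemar test is the sum over m = 0 to 26 of Bin(m; 26, 0.45) × P(two-sided exact p ≤ 0.05 given m discordant pairs), where each discordant pair favours NG with probability 0.425 / 0.45.
- Result: 90.8% at n = 26 and 89.3% at n = 25.

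The stated 90% is reproduced. For Part B it holds only if all 26 Untrained Users are in the analysed set.

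**2. Who meets the FAS rule as written.**

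| Group | Trained on a device | Performs simulations | In the FAS |
|---|---|---|---|
| Trained Users | Yes, by the PWD | Yes | Yes, including any who never simulate |
| PWDs | Yes, by site staff | No | Yes, if they count as subjects |
| Untrained Users | No | Yes | No |

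Part B in the FAS: 0 of 26 planned completers, and 0 of 33 at the maximum enrolment in Protocol Section 5.2.

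**3. Listed comparisons that involve Untrained Users.**

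- Success (SAP 9.5): 1 of 2.
- Time to administer (SAP 9.5): 3 of 4.
- Demographics (SAP 9.2): 2 of 2.
- Total: 1 + 3 + 2 = 6 of 2 + 4 + 2 = 8. On the FAS, the within-Part-B comparisons have no data and the trained-versus-untrained comparisons have one empty arm.

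**4. The GEE model.** The SAP's example code fits five parameters: intercept, training arm, device, arm-by-device, and first treatment received. Each user contributes two rows.

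- Both cohorts: (26 + 26) × 2 = 104 rows, design matrix rank 5.
- FAS as written: 26 × 2 = 52 rows. Arm is constant, so its column duplicates the intercept and the interaction column duplicates device. The rank is 3.

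Intercept, device and order can be estimated. Training and training-by-device cannot.

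**5. NG success for all users combined.** Planned NG simulations: 26 + 26 = 52. In the FAS: 26, all from Part A.

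**6. With membership defined by at least one simulation.** All 26 planned Part B users enter, the GEE rank returns to 5 of 5, and Part B exact power under the SAP's assumptions is the 90.8% from step 1. The primary test keeps 26 of 26 pairs under either wording.

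**The case against.** The strongest reply is that the harm is conditional. The SAP text assigns the FAS to no analysis, its intention to analyse Untrained Users is plain, and an empty run would be noticed at once. The Per Protocol definition has no training condition, so Part B completers can enter it. The table and figure shells, which are not available here, may name a set for each output. On this view the defect is a slip of wording.

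Much of that is fair. It probably is a slip, and the realistic result is uncertainty over Part B membership more than lost data. The count of 6 of 8 restates one exclusion several times; the two demographic comparisons involve essentially the same people, because everyone is due to use both devices. The GEE is declared exploratory. The PWD reading is literal and not the most natural one, since the SAP handles adverse events in associated persons separately. Trained Users who never simulate add no pair to McNemar.

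The objection does not repair the definition. Shells could name the FAS for a Part B table, but they would not change who is in it. Nor is the Per Protocol set a safe default. No section names it for Part B, and membership turns on judging the severity of deviations. Protocol Section 5.2 also ties completion to all scheduled procedures, while Section 5.1.3.2 withholds questionnaires from users who gave insulin or made no attempt. On one literal reading, those failures would count as non-completers and leave the set.

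**Conclusion.** The concern holds. The FAS as worded contains no Untrained Users, and nothing in either document corrects it. If the FAS is used, the first secondary hypothesis has 0 pairs, 6 of 8 listed comparisons lose an arm or all data, and the GEE loses 2 of its 5 parameters, the training terms it was specified to estimate. If it is not used, the SAP text gives no rule for what replaces it.

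These figures assume 26 completers per cohort and that being briefly shown a device is not training, which both documents support. The primary McNemar test and its power are not affected by this exclusion. This should be fixed, but it does not threaten the primary result.

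**What to change.** In SAP Section 8, define the FAS as all randomised Trained and Untrained Users who take part in at least one simulation. In Section 9.5, name the FAS as the set for the success analyses in both parts and for the GEE, and state where the Per Protocol set is used. Optionally, add that a questionnaire withheld under Protocol Section 5.1.3 does not make a participant a non-completer.

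The cost is a few words of SAP text, agreed before the first simulation, which is when SAP Section 3 requires sign-off. Sample size, data collection and the primary analysis do not change.
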